4.7.2 Adverse events

General common rules for adverse events

All adverse events (AEs) will be coded to a lower-level term (LLT), preferred term (PT), high-level term (HLT), high-level group term (HLGT), and associated primary system organ class (SOC) using the Medical Dictionary for Regulatory Activities (MedDRA) version in effect at Sanofi at the time of database lock.

Treatment-emergent adverse events (TEAEs) are AEs that developed, worsened, or became serious on or after the first administration of rFVIIIFc. Note that bleeding episodes in this patient population are not considered as AEs. Bleeding episodes that meet a serious criterion should be reported as serious adverse events (SAE). All bleeding episodes after the Baseline Visit will be captured in the EPD that the patient's parents/caregivers will maintain throughout the study period.

The primary focus of AE reporting will be on TEAEs.

An AE with incomplete or missing date/time of onset (occurrence, worsening, or becoming serious) will be classified as a TEAE unless there is definitive information to determine it is a pre-treatment or a post-treatment AE. (See [Section 5.3](#) for missing data handling.)

AEs and SAEs will be summarized for the following breakdowns:

- Overall (ITI, Tapering, and Follow-up periods combined)
- ITI period
- Post-ITI period (Tapering and Follow-up periods combined)
- Tapering period
- Follow-up period

Multiple occurrences of the same event in the same patient will be counted only once in the tables within a study period. When presented by severity, patients will be counted once for each SOC and preferred term based on the greatest severity within that SOC and preferred term,

respectively. Similarly, when presenting by relationship, patients will be counted once for each SOC and preferred term based on the highest relationship within that SOC and preferred term, respectively.

If the assessment of the relationship to rFVIIIFc is missing for an AE, this AE will be assumed as related to rFVIIIFc. If the severity is missing for the treatment-emergent occurrences of an AE, the severity will be imputed as severe.

The AE tables will be sorted as indicated in [Table 3](#).

Table 3 - Sorting of AE tables

AE presentation	Sorting rules
SOC and PT	SOCs and preferred terms within each SOC will be sorted alphabetically. ^a

^a The table of all TEAEs presented by SOC and PT will define the presentation order for all other tables (eg, treatment-emergent SAE) presented by SOC and PT, unless otherwise specified.

All adverse event listings will include the onset and resolution study days relative to Study Day 1, which is the date of the first rFVIIIFc treatment as well as the study period during which they occurred.

Analysis of all adverse events

An overview of number (%) of patients with TEAEs in the categories below will be generated (by study period and overall):

- Total TEAEs
- Patient with any TEAE
- Patient with at least one related TEAE
- Patient with any TEAE leading to permanent discontinuation of treatment or study
- Patient with any treatment emergent SAE (TESAE)
- Patient with at least one related TESAE
- Number of deaths

The AE summaries of [Table 4](#) will be generated with number (%) of patients experiencing at least one event.

Table 4 - Analyses of adverse events

Type of AE	MedDRA levels
All TEAEs	Primary SOC and PT
TEAEs by relationship to treatment	Primary SOC and PT
TEAEs by severity	Primary SOC and PT
Severe TEAEs	Primary SOC and PT
Treatment emergent SAEs	Primary SOC and PT

Analysis of deaths

Details on deaths on study will be tabulated in individual patient listing.

Analysis of adverse events of special interest (AESIs)

No adverse events of special interest (AESIs) were defined for this study.

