#### **5.4. Rationale for Dosing Regimen**

The proposed dose of rFVIIIFc for ITI (200 IU/kg/day [ $\pm 8$  hours]) is aligned with current ITI guidelines ([Valentino et al., 2015](#)). Since clearance is expected to be very rapid in the presence of inhibitors irrespective of the type of FVIII product, the high dose of 200 IU/kg/day evaluated in the International ITI Study will be used in the present study to achieve faster tolerization with fewer bleeding episodes. This dosing regimen is also supported by the results of a prospective clinical study that compared subjects treated with FVIII for ITI at a high dose (200 IU/kg/day) and a low dose (50 IU/kg 3 times per week). Results from this study ([Hay & DiMichele, 2012](#)) demonstrated that the times to achieve negative inhibitor titer, normal FVIII recovery, and FVIII tolerance were shorter in subjects treated with the high dose of FVIII compared with subjects treated with the low dose. Furthermore, subjects treated with the high dose of FVIII for ITI had a lower rate of intercurrent bleeding and fewer hospitalizations due to bleeding than subjects treated with the low dose of FVIII. Anecdotal unpublished reports of cases treated in the United States of America (USA) and Canada with 200 IU/kg/day also exist.

Furthermore, repeated doses of up to 1000 IU/kg evaluated in the nonclinical animal studies have shown no dose-limiting toxicities.

Sustained high FVIII activity levels in plasma (>150 to 200 IU/dL) may increase the risk of thrombotic events, although this risk is thought to be low. Therefore, FVIII activity levels in plasma will be monitored to provide a basis for dose adjustment of rFVIIIFc when needed. During the Tapering and Follow-Up Periods, the subject's dose will be adjusted to achieve a prophylactic dose (see Section [11.1](#)).

CONFIDENTIAL

The information contained herein may not be used, disclosed, or published without the written consent of Bioverativ Therapeutics Inc.

Page 35

VV-CLIN-0542000 3.0

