### **16.4.2. Methods of Analysis**

#### **16.4.2.1. Adverse Events**

Reported AEs during the study will be coded using Medical Dictionary for Regulatory Activities. The number and percentage of subjects with any AEs occurring after the first infusion of rFVIIIFc will be summarized in frequency tables by body system, preferred term, and maximum severity. Listings of serious SAEs and AEs leading to discontinuation will also be presented.

Tabulations of AEs and SAEs will be made separately for the ITI Period, the Tapering and Follow-Up Periods combined, as well as all 3 periods combined using ITIFAS and TPFAS, respectively. Tabulation for all AEs by relatedness across all periods will also be presented.

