1.1 STUDY DESIGN

This is an open-label, single-arm, interventional, multicenter study designed to explore the use of rFVIIIFc (recombinant coagulation factor VIII Fc fusion protein)([1](#))[\(2\)](#) for ITI (Immune Tolerance Induction). The study will be conducted in male patients of any age with severe hemophilia A and high-titer inhibitors (historical peak ≥ 5 BU/mL), who have been previously treated with any plasma-derived FVIII or recombinant conventional or EHL (extended half-life) FVIII and are undergoing ITI treatment for the first time.

The study period consists of 1) a 4-week (1-month) Screening Period; 2) a maximum of a 48-week (12-month) ITI Period; 3) a minimum of a 16-week (4-month) Tapering Period after all criteria for tolerization have been met; and 4) a 32-week (8-month) Follow-Up Period. Only patients who achieve ITI success will enter the Tapering and Follow-Up Periods. During the Tapering and Follow-Up Periods, the patient's dose will be adjusted to achieve the prophylactic dose. However, if FVIII peak activity levels rise above 200 IU/dL after the inhibitors are negative but before all the ITI success criteria are met, the dose may be adjusted according to Investigator judgment to maintain the FVIII peak activity levels between 100 and 200 IU/dL. This dose reduction will not be considered part of the Tapering Period, and the patient will maintain the schedule of assessments per the ITI Period.

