Patients' first and last doses and dosing frequencies during the tapering period, and the last prophylactic doses and dosing frequencies during the follow-up period will be summarized using TPFAS and FUPFAS, respectively.

Consumption

Total consumption of rFVIIIFc during the study (excluding use of study drug for the purpose of surgery, and for the assessment of IR and $t_{1/2}$) will be summarized descriptively using the ITIFAS. Analysis will also be conducted separately for each of the 3 treatment periods using their respective analysis set. Summary statistics of annualized total consumption will also be provided.

The rate for each patient will be annualized in order to account for difference in the duration of ITI treatment based on the equation below:

$$\text{Annualized total consumption} = \text{total consumption} * \frac{365.25}{\text{length in study (days)}}$$

Patients will be included in this analysis only if they were observed for at least 90 days.

Adherence

Overall adherence to dosing regimen of rFVIIIFc (excluding use for the purpose of surgery and for the assessment of IR and $t_{1/2}$) will be calculated in two ways as follows:

$$\text{Dose adherence (\%)} = \frac{\text{total dose administered as registered in diary and EDC}}{\text{total dose prescribed}}$$

$$\text{Frequency adherence (\%)} = \frac{\text{total number of days with infusions as registered in the diary and EDC}}{\text{total number of days on which infusion was prescribed}}$$

This calculation will be done for each study period, and the results will be listed and summarized descriptively using the respective analysis sets.

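### By-period adverse event percentages mix event rate with time in the period, because ITI ends at success and no rate per patient-year is planned

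*SAP*

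**What the plan says.** SAP 4.7.2 breaks AEs and serious AEs down into overall, ITI, post-ITI, Tapering and Follow-Up. The overview is described thus: "An overview of number (%) of patients with TEAEs in the categories below will be generated (by study period and overall". Apart from a total count of treatment-emergent AEs (TEAEs) and the number of deaths, its lines count patients. The tables by system organ class and preferred term "will be generated with number (%) of patients experiencing at least one event". Repeats are collapsed: "Multiple occurrences of the same event in the same patient will be counted only once in the tables within a study period".

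Protocol 16.4.2.1 takes the same approach: "The number and percentage of subjects with any AEs occurring after the first infusion of rFVIIIFc will be summarized in frequency tables", and "Tabulations of AEs and SAEs will be made separately for the ITI Period, the Tapering and Follow-Up Periods combined".

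The SAP design section gives "a maximum of a 48-week (12-month) ITI Period", then at least 16 weeks of Tapering and 32 weeks of Follow-Up. Only patients with ITI success enter the last two. Protocol 7.2.2 ends ITI at success or at 48 weeks.

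Elsewhere the SAP adjusts for time. For consumption (4.7.1) it says: "The rate for each patient will be annualized in order to account for difference in the duration of ITI treatment". Bleeding is annualized (4.4.1), and hospitalization days are expressed per year if at least 5 patients are available.

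**The concern.** The percentage of patients with at least one event rises with time observed, even at a constant event rate. Here the time is not fixed by design. ITI duration is in effect the primary outcome, so faster tolerization shortens the ITI Period and lowers the percentage recorded there, while slow responders raise it. A reader who sets the ITI column beside the post-ITI column is partly reading efficacy.

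AEs and serious AEs are a named secondary endpoint, and the dose differs between periods, so readers are likely to look across the columns. The SAP accepts the need for time adjustment for consumption and bleeding but does not apply it to AEs.

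**Working it through.** The documents state no AE rate, so there is no figure of the plan's to reproduce. What follows is illustrative.

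**Period lengths**
- Fastest ITI success on the protocol's visit schedule: first negative titer at Week 2, confirmation and first incremental recovery at Week 4, second recovery at Week 6, half-life at Week 8, first tapering visit two weeks later at Week 10. SAP 4.1 ends ITI the day before the first tapering visit, so about 10 weeks.
- Longest ITI treatment: 48 weeks.
- Tapering at least 16 weeks, Follow-Up 32, combined about 48.
- Ratios: longest ITI to shortest Tapering 48/16 = 3.0; longest ITI to Follow-Up 48/32 = 1.5; longest ITI to post-ITI 48/48 = 1.0; longest to shortest ITI 48/10 = 4.8.

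**Formula**

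Assume a constant rate r per patient-year over T weeks. Expected share with at least one event = 1 − exp(−r × T × 7/365.25).

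| Rate r | 10 wk | 16 wk | 17 wk | 32 wk | 48 wk |
|---|---|---|---|---|---|
| 0.25 | 4.7% | 7.4% | 7.8% | 14.2% | 20.5% |
| 0.5 | 9.1% | 14.2% | 15.0% | 26.4% | 36.9% |
| 1 | 17.4% | 26.4% | 27.8% | 45.8% | 60.1% |
| 2 | 31.8% | 45.8% | 47.9% | 70.7% | 84.1% |
| 4 | 53.5% | 70.7% | 72.8% | 91.4% | 97.5% |

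**A difference that is not there.** At r = 1 throughout, 48 weeks of ITI gives 60.1% and a 16-week taper 26.4%, a ratio of 60.1/26.4 = 2.3. For a patient tolerized at 17 weeks (two of the three case reports in protocol 5.2.3 with a time to tolerization took 17 and 18 weeks), equal rates of 1 give 27.8% in ITI against 60.1% over 48 weeks post-ITI.

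**A difference that is hidden or reversed.** With r = 1.0 in a 16-week ITI and 0.5 over 48 weeks post-ITI, the table shows 26.4% against 36.9%. The percentages are equal when the rate ratio equals the inverse ratio of lengths: 48/24 = 2.0 for a 24-week ITI and 48/17 = 2.8 for a 17-week ITI. So if all ITI periods were of one length, a doubled ITI rate would look equal at 24 weeks and lower below that, whatever the absolute rate.

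**A mixed cohort.** Suppose 10 of 17 patients succeed at 17 weeks and 7 stay 48 weeks, with a true ITI rate of 2 and a post-ITI rate of 1. ITI percentage = (10 × 0.479 + 7 × 0.841)/17 = 62.8%; post-ITI = 60.1%. The doubling is barely visible.

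**With rates.** Patient-years in that cohort: ITI (10 × 17 + 7 × 48)/52.18 = 9.7; post-ITI 10 × 48/52.18 = 9.2. Expected events are 2 × 9.7 and 1 × 9.2, so the expected rates are 2 and 1 and the ratio of 2 is recovered.

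**Precision.** At rates of 1.0 and 0.5 the same patient-years give about 10 and 5 events. Exact Poisson 95% intervals are about 0.49 to 1.90 and 0.18 to 1.27 per patient-year, which overlap widely.

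**The case against.** The strongest reply is that nothing in the plan sets out to compare periods on AEs. The safety objective is descriptive, the study has one arm and no tests, and protocol 16.1 allows at most 17 patients. The SAP also supplies some of the pieces: each patient's duration in each period (4.3.4), dosing duration and exposure days by period (4.7.1), a total TEAE count, and AE listings with onset day and period. Hospitalizations are captured as serious AEs (protocol 13.4), so hospitalization days per year partly cover serious events. The annualization precedent is imperfect too, since it leaves out patients observed for under 90 days.

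Much of this stands and limits the point to descriptive reading. It does not dispose of it. Section 4.7.1 measures first to last dose rather than time observed, and the planned tables give no event counts for related TEAEs or treatment-emergent serious AEs (TESAEs). A reader would have to rebuild the rates from listings.

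A reader might infer that these tables will mislead about thrombosis under high-dose ITI. The documents do not support that. Protocol 5.4 says sustained high factor VIII activity "may increase the risk of thrombotic events, although this risk is thought to be low", and it expects very rapid clearance while inhibitors are present, so the ITI dose does not imply high activity throughout ITI. The target activity range in protocol 11.1 applies both to dose adjustment late in ITI and to early Tapering. A by-period rate would therefore not isolate time at high activity either.

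**Conclusion.** The point holds as a reporting weakness in a secondary endpoint. The by-period percentages mix event rate with time in the period, and the mixing matters mainly when ITI ends early through success. It can make equal rates look 2.3-fold apart (longest ITI against shortest taper) or make a doubled ITI rate look lower than the post-ITI rate (ITI shorter than 24 weeks against 48 weeks post-ITI).

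It would go too far to say that ITI and prophylaxis differ several-fold in planned length: at the maxima the ratio is 1.0 against combined post-ITI and 1.5 against Follow-Up. Nor would rates make the contrast a fair comparison of treatments. Only successes contribute post-ITI time, and inhibitor relapse is by definition a serious AE that can occur only after ITI success (protocol 15.1.1 and 15.3.2).

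The sizes rest on assumed constant rates, assumed ITI durations and full 48-week post-ITI follow-up.

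**What to change.** In SAP 4.7.2, keep the number (%) tables and add the following for each period and overall:

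- Patient-years of observation using the SAP 4.1 period boundaries, the number of events, and events per patient-year, for total TEAEs, related TEAEs, TESAEs, and the allergic and thrombotic events of protocol 15.3.2.
- A statement that the rate numerator counts all events, so the once-per-period rule does not apply to it, with the number of patients contributing events.
- An interval that allows for clustering within patients, since one patient with many events could dominate. Alternatively, use an exact Poisson interval on first events per patient, with time censored at the first event.
- TESAE rates with and without inhibitor relapse, or relapse excluded from any ITI against post-ITI rate.
- The ITI rate restricted to patients who entered Tapering.
- A sentence saying that rates remove the effect of duration but not the selection of successes into later periods, so comparisons between periods remain descriptive.

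The cost is SAP wording and one added block of output. Period boundaries are already defined and AE onset days are already listed, so no new data or visits are needed. The downside is wide intervals with up to 17 patients and reliance on a roughly constant rate within each period.

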4.7.3 Additional safety assessments

4.7.3.1 Laboratory variables and vital signs

The following laboratory variables and vital signs variables will be reported.

- Hematology:
 - Red blood cells and platelets and coagulation: hemoglobin, hematocrit, red blood cell count, platelet count
 - White blood cells: white blood cell count, neutrophils, lymphocytes, monocytes, basophils, eosinophils
- Blood chemistry:
 - Metabolism: glucose, total protein
 - Electrolytes: sodium, potassium, chloride
 - Renal function: serum creatinine, blood urea nitrogen
 - Liver function: alanine aminotransferase, aspartate aminotransferase, alkaline phosphatase, gamma glutamyl transferase, total bilirubin
- Urinalysis:
 - Dipstick urinalysis, including a protein reading; if the protein reading is positive ($\geq 1+$), a full laboratory urinalysis will be performed.
- Vital signs: systolic and diastolic blood pressure, pulse rate, respiratory rate, and body temperature

Quantitative analyses

For all laboratory variables, local laboratory results are reported by the site and captured in the eCRFs. Central laboratory data are not collected for this study. Shifts in normality status of blood chemistry and hematology from baseline to post-baseline and minimum/maximum post-baseline values, respectively, will be provided.

For vital signs, descriptive statistics for results and changes from baseline/pre-injection will be provided by study period and time point (prior or after rFVIIIFc infusion).

4.8 OTHER ANALYSES

4.8.1 PK analyses

Some of the pharmacokinetic parameters are considered exploratory endpoints ([Section 4.5.1](#)). Values of all pharmacokinetic parameters will be tabulated in individual patient data listings. No summary statistics will be provided because the pharmacokinetic profiles are anticipated to be idiosyncratically different depending on status of immunotolerance of each patient. Values of pharmacokinetic parameters will be tabulated in individual patient data listings.

4.8.2 Immunogenicity analyses

See [Section 4.5](#).

4.8.3 Physical Examination

A general physical examination will be assessed and recorded as “normal” or “abnormal” at each visit. Abnormalities will be specified. Any persisting abnormalities will be stated each time the examination is performed. Diagnosis of new abnormalities will be recorded as AEs. If any abnormalities are reported at the Screening Visit, they will be recorded as medical history.

The number and percentage of patients with physical examination abnormalities at screening (or baseline if a screening exam is not available) will be presented by body system for ITIFAS. Percentages will be based on the number of patients for whom a screening/baseline physical examination is available. On-treatment physical examination findings will be listed.

4.8.4 Surgery

Patients who plan to have major surgeries are not to be enrolled in the study. Information on minor surgeries collected in the study including the type and reason of surgery, and date/time of surgery will be tabulated in individual patient data listings.

4.9 INTERIM ANALYSES

An interim analysis (IA) is planned for when at least 10 patients have completed at least 24 weeks (6 months) of ITI treatment. Subsequent interim analyses, if conducted, will depend on the number of years required to recruit the targeted number of patients.

5 SUPPORTING DOCUMENTATION

5.1 APPENDIX 1 LIST OF ABBREVIATIONS

ADA:	anti-drug antibodies
AE:	adverse event
AESIs:	adverse events of special interest
EDC:	electronic data capture
EHL:	extended half-life
EOS:	end of study
EPD:	electronic patient diary
FUPFAS:	follow-up period full analysis set
HLT:	high level term
IR:	incremental recovery
ITI:	immune tolerance induction
ITIFAS:	ITI full analysis set
LLT:	lower-level term
MedDRA:	medical dictionary for regulatory activities
PT:	preferred term
rFVIIIFc:	recombinant coagulation factor VIII Fc fusion protein
SAE:	serious adverse event
SAP:	statistical analysis plan
SD:	standard deviation
SOC:	system organ class
TEAE:	treatment-emergent adverse event
TESAE:	treatment emergent SAE
TPFAS:	tapering period full analysis set
WHO-DD:	World Health Organization-drug dictionary

5.2 APPENDIX 2 DEMOGRAPHICS AND BASELINE CHARACTERISTICS, PRIOR OR CONCOMITANT MEDICATIONS

Demographics, baseline characteristics, medical surgical history

The following demographics and baseline characteristics, medical and surgical history, and disease characteristics at baseline will be summarized using descriptive statistics in the ITIFAS population.

Demographic and baseline characteristics

- age in years as quantitative variable*
- gender (Male, Female)
- race (White, Black or African American, Other)

- ethnicity (Hispanic or Latino, not Hispanic or Latino)
- weight (kg) at Baseline
- height (cm) at Screening

* In the eCRF, age is reported in the unit of week for patients who are \leq 2 years of age and in year for those who are $>$ 2 years of age. For purpose of the reporting, all ages will be converted to the same unit of year. Data which are reported in week will be divided by 52.

Baseline safety and efficacy parameters (apart from those listed above) will be presented along with the safety and efficacy summaries.

Number and percentages of patients reporting medical and surgical history will be summarized by body system and preferred term. A patient is counted only once if they report more than one occurrence of medical or surgical history in the same body system. Detailed information on diagnosis and current status associated with a specific history will be provided in a data listing for each patient.

Hemophilia history for time from diagnosis of hemophilia, lowest documented FVIII activity value, presence of family history of inhibitor, blood type, genotype, vaccination within last year will be summarized with descriptive statistics. Bleeding history on the numbers of bleeds per month in the 3 months prior to inhibitor diagnosis and from inhibitor diagnosis to the onset of ITI treatment will be summarized by type as well as overall. Inhibitor history on time from inhibitor detection to the onset of ITI treatment, time from first FVIII treatment to first inhibitor detection, peak historical inhibitor level, number of exposure days at first confirmed inhibitor development, and inhibitor titer prior to ITI initiation will be summarized. The last FVIII treatment and bypassing agent used prior to the study will be summarized by type and regimen.

Prior or concomitant medications

All medications will be coded using the World Health Organization-Drug Dictionary (WHO-DD) using the version currently in effect at Sanofi at the time of database lock.

- Prior medications are all drugs and substances the patient used prior to the first administration of rFVIIIFc. Prior medications can be discontinued before the first administration or still ongoing during the treatment period.
- Concomitant medications are any interventions received by the patient concomitantly to the rFVIIIFc up through the EOS visit. Note that a medication started prior to the first dose of rFVIIIFc and was ongoing during and/or after the first dose of rFVIIIFc will be classified as both prior and concomitant.
- Post-treatment medications are those the patient took in the period running from the end of the concomitant medications period up to the Follow-Up visit/phone call.
- Medications with a start date after the follow-up visit will not be considered concomitant and will not be included in the summary tables.

- A given medication can be classified as a prior medication and/or as a concomitant medication and/or as post-treatment medication. If it cannot be determined whether a given medication was taken prior or concomitantly or post, it will be considered as prior, concomitant, and post-treatment medication.

If a concomitant medication start day is missing or partial, the medication will be assumed to be both a prior and a concomitant medication unless it can be deduced from the partially recorded medication start or stop dates whether a medication is concomitant or prior. See [Section 5.3](#) for handling of missing or partial dates.

The prior and concomitant and post-treatment medications will be summarized for the ITIFAS population. Summaries will be based on the number and percentage of patients taking medications by WHODRUG standardized medication text. Within each WHODRUG standardized medication text a patient will be counted once even if he reported taking the medication more than once. Separate summaries will be provided for prior and concomitant medications. Medications taken after the EOS visit up to the Follow-Up visit/phone call will not be included in the summary table of concomitant medications. Two listings will be provided, one for prior and concomitant medications taken through the EOS visit and the other for the post-treatment medications taken after the EOS visit and prior to the Follow-Up visit/phone call. The summaries will be sorted in alphabetical order.

In this study, for patients who receive breast milk, maternal concomitant medications are also be collected at the same time points as other concomitant therapies, unless the breast milk is derived from a source other than the mother or the mother did not consent. These will be presented in a similar way as other concomitant medications.

Bypassing agents

Number and percentage of patients who used bypassing agents (aPCC [FEIBA] or rFVIIa [NovoSeven]) prior to first dose of ITI with rFVIIIFc and during each of the study periods will be tabulated by type of bypassing agents and regimen (on-demand versus prophylaxis). Total consumption of bypassing agents will be tabulated by type of bypassing agents and by study period as well as combined. Information from different data sources, e.g., concomitant medications, ePD and in-clinic use, will be integrated for this analysis.

Other therapies and procedures

Other therapies administered and concomitant procedures performed within 30 days prior to the first dose of study drug through the end of the study will be listed only, a summary table is not planned.

